6.5. POOLING OF CENTERS

Subjects will not be pooled based on site size, but rather by country, to ensure a sufficient number of subjects per treatment arm in both ITT and PP populations for analysis that contain country as a model effect. Pooling by country will not be performed if the number of subjects at Canadian sites comprises less than 5% of enrolled subjects. Otherwise, pooling by country will be performed.

1007728

7. DEMOGRAPHIC, OTHER BASELINE CHARACTERISTICS AND MEDICATION

7.1. SUBJECT DISPOSITION AND WITHDRAWALS

Subject disposition data will be listed. A disposition table will present, by treatment group and overall, the number and/or percentage of subjects who signed the informed consent and entered the study (i.e., were screened, screen failed prior to Run-in, screen failed during the Day -14 to Day -1 Run-in, and randomized), complete the study drug, discontinued study drug, completed the study, and discontinued from the study after randomization. The reasons for early withdrawal after randomization will be summarized. A separate table will display the number of subjects who met eligibility criteria at screening and washout period but withdrew prior to randomization (non-randomized subjects) with a summary of the reasons for withdrawal prior to randomization.

Assignment to the analysis sets (safety, ITT, and PP) will be summarized.

7.2. SUBJECT ELIGIBLITY AND PROTOCOL DEVIATIONS

All subjects, including screen failure subjects, who violate the Inclusion/exclusion criteria will be listed. Reason for screen failure will be summarized.

Deviations that could affect the primary and secondary variables will be considered when determining a subject's eligibility for the PP population. The number and percent of subjects who had any major deviation and each type of major protocol deviation will be tabulated for the ITT Analysis Set.

7.3. DEMOGRAPHIC AND OTHER BASELINE CHARACTERISTICS

Demographic characteristics include age, gender, race, ethnicity and country of investigational site. Baseline characteristics will include HbA1c, blood pressure, body weight, BMI, FPG, duration of diabetes from diagnosis to the date of informed consent, and stratification factors including HbA1c values at V5 and background anti-diabetic treatment status (treatment naïve or not). Summary descriptive statistics by treatment will include counts and percentages for discrete variables and estimation of means, standard deviations, medians, inter-quartile range (Q1, Q3), minimum, and maximum for continuous variables. Subjects' baseline demographic and personal baseline characteristics will be summarized by treatment group and overall for subjects in the safety, ITT, and PP analysis set. Subject age will be calculated as:

Age at Study day 1 = (date of informed consent - date of birth + 1) / 365.25 and round down to complete years.

1007728

7.4. MEDICAL HISTORY

Significant medical and surgical history, including dates of diagnoses and procedures and whether the condition is ongoing, if applicable, will be collected. Each condition will be recorded as a verbatim term, date of onset, date resolved, and a checkbox that indicates ongoing conditions. Significant surgical and medical history will be coded using the Medical Dictionary for Regulatory Activities (MedDRA) version 19.0.

Medical and surgical history will be summarized for the Safety Analysis Set by treatment group, system organ class (SOC), and MedDRA preferred term (PT), overall. Subject data will be listed.

Subject diabetes and cardiovascular diseases history will be summarized for all categorical variables by frequency and percentage. Listing will be provided.

7.5. MEDICATION

All prescription and over-the-counter medications, including vitamins and herbal supplements, that subjects receive during the trial must be documented on the CRF. The medication name, dose, frequency, route of administration, date(s) of administration and reason for administration must be recorded. This documentation should continue through the treatment period and the follow up period. Changes from baseline anti-hypertensive therapy and their rationale must be recorded in the CRF.

All medication will be coded using the World Health Organization Drug Dictionary (WHO-DD) version March 2016. Preferred drug name, Anatomical/Therapeutic/Chemical (ATC) class will be reported for inclusion in the database.

Medication summaries based on ATC level 2, and the preferred drug names will be produced for the Safety Analysis Set. The summaries will present, by treatment group, the frequency and percentage of subjects who used any medication in an ATC class, or any medication based on a single preferred drug name. Medication summaries will be sorted by descending total frequency of ATC class and by PT within ATC class. Subjects will be counted only once for each medication class and each preferred drug name.

For subject listings, medications will be reported based on ATC class and PT; multiple medications for an individual subject will be listed by start date and then by stop date, from earliest to latest medications.

1007728

7.5.1. Prior Medication

Any medication with a start date prior to or on first dose date for the double-blind treatment period will be considered a prior medication. If the entire start date of a given medication is missing, then the medication will be considered as prior medication.

No summary for prior medication will be presented. Prior and concomitant medications will be presented together on a single listing. The listing will be ordered by subject number, and medication start/end dates. Prior medication will be flagged.

7.5.2. Concomitant Medication

A concomitant medication is any medication that the subject has been taking prior to the first dose of double blind study medication and that the subject is expected to continue to take for some portion of the study treatment period, as well as any medication other than the investigational product that the subject takes during the course of the study treatment period. In the case of completely missing stop date, medication will be assumed to be concomitant. A medication can be both prior and concomitant.

The medications or treatment for controlling hypoglycemia must be recorded as concomitant medications in the CRF. Any medication given to treat hyperglycemia and continued for more than 2 weeks during the treatment period is considered a rescue therapy and should be recorded in the concomitant medication log. All medication given to treat hyperglycemia will be recorded in CRF.

Concomitant medications will be presented in a summary table as well as in a subject listing. Rescue medications will be summarized in a separate table and flag in the same listing.

1007728

8. **EFFICACY**

Efficacy data include HbA1c, FPG, body weight, and blood pressure. All changes from baseline will be calculated as the post-treatment value minus the last non-missing assessment before randomization (Visit V5). All continuous efficacy data will be summarized for observed and change values by treatment and visit. Proportion of subjects with HbA1c of < 7% will be summarized by frequency and proportion by treatment and visit.

PRIMARY EFFICACY ENDPOINT AND ANALYSIS 8.1.

The primary efficacy hypothesis is that bexagliflozin reduces HbA1c after 24 weeks of treatment when compared to placebo.

8.1.1. **Primary Efficacy Analysis**

Let $\mu_{Bexagliflozon}$ and μ_{PBO} represent the mean changes from baseline in HbA1c at Week 24 for bexagliflozin and placebo arms, respectively. The following hypotheses will be tested:

 H_0 : $\mu_{\text{Bexagliflozon}} = \mu_{\text{PBO}} \text{ versus } H_1$: $\mu_{\text{Bexagliflozon}} \neq \mu_{\text{PBO}}$

This hypothesis will be tested based on ITT analysis set using all observed data and a mixed model repeated measures (MMRM) approach. The MMRM model will include terms for background anti-diabetes treatment status (treatment naïve or not), treatment, visit, treatment-by-visit interaction and the baseline HbA1c value as a fixed effect covariate. Country will be used as a fixed effect if pooling by country is used. The analysis will evaluate the mean change from baseline in HbA1c over the 24-week double-blind treatment period. An unstructured covariance will be used to model the within-subject correlation. The Kenward-Roger approximation will be used to estimate denominator degrees of freedom. If the model with the unstructured covariance structure does not converge, an autoregressive(1) covariance structure will be used. HbA1c values obtained after the start of rescue medication will not be excluded from the analysis.

Based on the MMRM model, the treatment and treatment-by-visit interaction terms allow for comparisons of the treatment groups at each visit, and over week 6 to week 24. Least squares (LS) mean treatment differences between the bexagliflozin group and the placebo group at week 24 will be estimated from the model with the corresponding p-values and their two-sided 95 % CIs presented. Sample SAS code will be provided in Appendix 1.

Descriptive statistics (n, mean, Q1, median, Q3, SD, minimum, and maximum) will be reported by treatment group and visit, along with the least squares means, differences

1007728

between LS means, a 2-sided 95% confidence interval for each difference, p-values from the model effects. In addition, the LS means with standard errors of the change from baseline over time and difference between treatment groups with 95% will be presented graphically for the ITT population.

For supportive analyses, the primary efficacy endpoint will be analyzed with observed available data using the PP analysis set in a similar manner as above.

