The key secondary measures will be the changes from baseline to week 24 of systolic blood pressure and body weight. The exploratory secondary measures will be the change from baseline of the fasting plasma glucose concentration over time, the change from baseline of HbA1c over time, and the proportion of subjects who achieve an HbA1c < 7% over time.

Safety Assessments:

The safety of bexagliflozin will be assessed over the 24-week treatment phase. Adverse events (AEs) of special interest include genital and urinary tract infections, diuretic effects, hepatotoxicity, MACE, hypoglycemia, fractures, malignancy, hypersensitivity reactions, hypotensive episodes, acid-base disorders, renal failure events, and amputations.

Statistical Methods:

Data summaries will report descriptive statistics (number of subjects [n], mean, standard deviation [SD], Q1, median, Q3, minimum, and maximum for continuous variables, and frequency and percentage for categorical and ordinal variables. If there are missing values, the number missing will be presented, but without a percentage. All data collected will be included in by-subject data listings.

The primary efficacy hypothesis is that bexagliflozin reduces HbA1c after 24 weeks of treatment when compared to placebo. The analysis of the change in HbA1c at week 24 will be based on ITT Analysis Set using all observed data and a mixed model repeated measures (MMRM) approach that will include terms for treatment, visit, treatment-by-visit interaction and randomization stratification factors as fixed effects and the baseline HbA1c value as a fixed effect covariate. Least squares mean treatment differences between the bexagliflozin group and the placebo group at week 24 will be estimated from the model with the corresponding p-values and their two-sided 95% CI presented. An unstructured covariance will be used to model the within-subject correlation. If the model with the unstructured covariance structure does not converge, an autoregressive(1) covariance structure will be used. HbA1c values obtained after the start of rescue medication will not be excluded from the analysis.

The MMRM model is one approach to obtain treatment effect estimates in the presence of missing data. As sensitivity analyses for missing data, the following will be performed on the ITT analysis set:

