5.4 Method of Assigning Subjects to Treatment Groups

Eligible subjects who complete the run-in period and meet all study inclusion/exclusion requirements will be randomized in a 2:1 ratio to receive once daily bexagliflozin tablets, 20 mg or bexagliflozin tablets, placebo during the 24-week treatment period. Subjects will be assigned to treatment groups in sequential order as they qualify for the study, using a centrally located and managed Interactive Web Response System (IWRS). Randomization will be stratified according to HbA1c measured at the last assessment prior to randomization (Visit V5) (HbA1c at 7.0 to 8.5% or 8.6 to 10.5%) and background anti-diabetic treatment status (treatment-naïve or on treatment).

The study will be conducted at multiple investigative sites and will likely involve a variable numbers of subjects at each site. Enrollment will be on a competitive basis but each site will

be capped at 21 randomized subjects. However, when a site reaches 21 randomized subjects, if a potential subject at that site is in washout or run in already and wishes to continue with the study, the subject will be allowed to continue and, if eligible, to be randomized. Subject randomization will be deactivated for all sites when the planned number of subjects has been enrolled. However, if a potential subject is in washout or run in already and wishes to continue with the study, the subject will be allowed to continue and, if eligible, to be randomized.

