9.5.1 Primary Efficacy Endpoint

The primary efficacy hypothesis is that bexagliflozin reduces HbA1c after 24 weeks of treatment when compared to placebo. The analysis of the change in HbA1c at week 24 will be based on ITT Analysis Set using all observed data and a mixed model repeated measures (MMRM) approach that will include terms for treatment, visit, treatment-by-visit interaction and randomization stratification factors as fixed effects and the baseline HbA1c value as a

fixed effect covariate. Least squares mean treatment differences between the bexagliflozin group and the placebo group at week 24 will be estimated from the model with the corresponding p-values and their two-sided 95 % CI presented. An unstructured covariance will be used to model the within-subject correlation. If the model with the unstructured covariance structure does not converge, an autoregressive(1) covariance structure will be used. HbA1c values obtained after the start of rescue medication will not be excluded from the analysis.

Sensitivity analyses will be performed as:

- 1. A multiple imputation method will be used to impute missing observations (including observations obtained after rescue medication) in the ITT Analysis Set prior to carrying out the MMRM analysis.
- 2. A multiple imputation method will be used to impute missing observations (not including observations obtained after rescue medication) in the ITT Analysis Set prior to carrying out the MMRM analysis.
- 3. A last observation carried forward (LOCF) method will be used to impute the missing observations in the ITT Analysis Set prior to carrying out the MMRM model.

For supportive analyses, the primary efficacy endpoint will be analyzed with observed available data using the PP analysis set in a similar manner as above.

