3.4. BRIEF DESCRIPTION

THR-1442-C-450 is a multi-center, randomized, double-blind, placebo-controlled, parallel-group study. It is designed to compare the efficacy and safety of once daily oral administration of bexagliflozin tablets, 20 mg to bexagliflozin tablets, placebo, in treatment-naïve type 2 diabetic subjects or subjects previously treated with no more than one oral hypoglycemic agent (OHA).

All eligible subjects will start a 2 week placebo run-in period. Subjects who miss no more than one dose of the run-in medication, have fasting blood glucose values \geq 250 mg/dL on no more than two consecutive days, and who, at the baseline visit (Visit V5), have an HbA1c level between 7 and 10.5% and a fasting glucose level < 250 mg/dL will be eligible for randomization.

Approximately 210 subjects will be randomly assigned to receive oral bexagliflozin tablets, 20 mg or placebo, in a 2:1 ratio once daily for 24 weeks in an out-patient setting. Subjects with uncontrolled hyperglycemia based on blood glucose levels may receive additional approved anti-diabetic medications. Treatment group assignment at the start of the treatment period will be stratified by HbA1c level at the start of the run-in period (7.0 to 8.5% or 8.6 to 10.5%) and background anti-diabetes treatment status (treatment naïve or not).

Each subject will be contacted by telephone at week 2 (Visit V7) for safety monitoring and will be instructed to return to the clinic at weeks 6, 12, 18, and 24 (Visits V8, V9, V10, V11) for efficacy assessment and safety monitoring. Subjects will return to the clinic for a follow-up visit at week 26 or two weeks after the last dose of investigational product if the subject terminates prior to week 24 (Visit V12).

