3.7. TREATMENT ASSIGNMENT & BLINDING

3.7.1. Treatment Assignment

Eligible subjects who complete the run-in period and meet all study inclusion/exclusion requirements will be randomized in a 2:1 ratio to receive once daily bexagliflozin tablets, 20 mg or bexagliflozin tablets, placebo, during the 24-week treatment period. Subjects will be assigned to treatment groups in sequential order as they qualify for the study, using a centrally located and managed Interactive Web Response System (IWRS). Randomization will be stratified according to HbA1c measured at the last assessment prior to randomization (Visit V5) (HbA1c at 7.0 to 8.5% or 8.6 to 10.5%) and background anti-diabetic treatment status (treatment-naïve or on treatment).

Potential study subjects will be screened and assigned a subject number. Once all screening procedures are completed and the study eligibility is confirmed by the investigator, the randomization numbers will be allocated to subjects within the

1007728

appropriate treatment group by the randomization system. Once a screening or randomization number has been assigned, it will not be re-used in any event. No subjects will be randomized into the study more than once. If a randomization number has been allocated incorrectly, no attempt will be made to remedy the error once study medication has been dispensed. The subject will continue with the randomization number and study medication. The study staff will notify the Sponsor Contact as soon as the error is discovered without disclosing the study medication administered. Admission of subsequent eligible subjects will continue using the next unallocated number in the sequence.

The study will be conducted at multiple investigative sites and will likely involve a variable numbers of subjects at each site. Enrollment will be on a competitive basis but each site will be capped at 21 randomized subjects. However, when a site reaches 21 randomized subjects, if a potential subject at that site is in washout or run in already and wishes to continue with the study, the subject will be allowed to continue and, if eligible, to be randomized. Subject randomization will be deactivated for all sites when the planned number of subjects has been enrolled. However, if a potential subject is in washout or run in already and wishes to continue with the study, the subject will be allowed to continue and, if eligible, to be randomized.

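### The SAP's primary MMRM omits the HbA1c randomisation stratum that the protocol includes and adds a conditional country term, yet SAP 12 declares no change

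*SAP*

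**What the plan says.** **Randomisation.** Under Protocol 5.4, assignment is "stratified according to HbA1c measured at the last assessment prior to randomization (Visit V5) (HbA1c at 7.0 to 8.5% or 8.6 to 10.5"%), and also by background treatment status. SAP 3.7.1 agrees: "Randomization will be stratified according to HbA1c measured at the last assessment prior to randomization (Visit V5"). SAP 3.4, with the same wording in Protocol 3.1, dates the factor differently: "stratified by HbA1c level at the start of the run-in period (7.0 to 8.5% or 8.6 to 10.5"%).

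**Primary model in the protocol.** Section 9.5.1 lists treatment, visit, "treatment-by-visit interaction and randomization stratification factors as fixed effects and the baseline HbA1c value". The synopsis repeats this: "treatment-by-visit interaction and randomization stratification factors as fixed effects and the baseline HbA1c value as a fixed effect covariate".

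**Primary model in the SAP.** Section 8.1.1 states: "The MMRM model will include terms for background anti-diabetes treatment status (treatment naïve or not), treatment, visit, treatment-by-visit interaction and the baseline HbA1c value". It then adds: "Country will be used as a fixed effect if pooling by country is used". The trigger is in SAP 6.5: "Pooling by country will not be performed if the number of subjects at Canadian sites comprises less than 5% of enrolled subjects".

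**LOCF model.** SAP 8.1.2 says the LOCF data go through the same MMRM, but the terms it then lists are background status, treatment and baseline HbA1c only.

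**Standing of the two documents.** Protocol 9.1 makes the SAP the final plan. SAP 12 declares that no planned analysis differs from the protocol.

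**The concern.** The protocol asks for both stratification factors and, separately, continuous baseline HbA1c. The SAP keeps one factor and the continuous value. Because the SAP governs, the primary test as written runs without one of the two factors used to randomise, and possibly with a country term that no efficacy model in the protocol contains. A reader who relies on SAP 12 would take this for the protocol's model.

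The two documents therefore define two primary p-values, and that p-value decides whether systolic blood pressure and body weight may be tested at all. What is at stake is one correctly declared confirmatory model that matches the randomisation.

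**Working it through.** **1. The plan's own figure.** Inputs from Protocol 9.2 and SAP 3.6: difference 0.5, SD 1.0, two-sided alpha 0.05, 128 and 64 evaluable subjects. The standard error is √(1/128 + 1/64) = 0.1531 and 0.5/0.1531 = 3.266, so power is about Φ(3.266 − 1.960) = 90.4%; the exact noncentral t gives 90.1%. The stated 90% is reproduced. This calculation uses no covariates, so it does not depend on the disputed terms.

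**2. Terms side by side.**

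| Term | Protocol 9.5.1 and synopsis | SAP 8.1.1 | SAP 8.1.2 LOCF list |
|---|---|---|---|
| Treatment | yes | yes | yes |
| Visit, treatment-by-visit | yes | yes | not listed |
| Background treatment status | yes | yes | yes |
| V5 HbA1c stratum | yes | **no** | **no** |
| Continuous baseline HbA1c | yes | yes | yes |
| Country | no | **conditional** | not listed |

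**3. Country trigger.** If enrolled means the 210 randomised, 5% is 0.05 × 210 = 10.5, so 11 or more Canadian subjects bring the term in. The trigger depends on recruitment, not on outcome.

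**4. Which HbA1c defines the stratum.** The synopsis, Protocol 3.2.1 and 5.4, and SAP 3.7.1 say V5. Protocol 3.1 and SAP 3.4 say the start of run-in, which is V4. Protocol Appendix 2 schedules glycaemic tests at V1 and V5 and none at V4, so V5 is the only workable reading.

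**5. Other differences that SAP 12 does not declare.**
- SAP 8.2.1 applies the sensitivity analyses, including imputation, to the key secondary endpoints. Protocol 9.5.2 rules out imputation for endpoints other than the primary.
- SAP 8.1.2 carries forward the HbA1c recorded at rescue in the LOCF analysis. Item 3 of Protocol 9.5.1 fills in missing observations only.
- SAP 5.2 groups safety data by the first kit dispensed. Protocol 9.3.2 groups by the medication taken.

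This covers the models, missing-data analyses and safety grouping only; it is not a full comparison of the documents.

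**6. Numerical size.** The documents give no baseline distribution, no step in outcome at the 8.5/8.6 cut and no country effect, so these are assumptions.

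*MMRM simulation*, 12 scenarios of 2,000 trials: 210 randomised 2:1 in stratified blocks, 10% random dropout, unstructured covariance, approximate degrees of freedom in place of Kenward-Roger. Assumed: residual SD 0.95; within-subject correlations 0.6–0.8; baseline slope −0.3; 60% pre-treated; baseline N(8.1, 0.9) or N(8.5, 1.0) truncated to 7.0–10.5; step 0, ±0.3 or +0.5; Canada 10% with effect 0.2, or 30% with effect 0.3.

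| | Protocol model | SAP, no country | SAP with country |
|---|---|---|---|
| Change in Week 24 SE | reference | −0.1% to +0.9% | −0.9% to +0.9% |
| SD of shift in estimate (percentage points) | reference | 0.007–0.019 | 0.015–0.024 |
| Power at −0.5 | 92.1–94.3% | 91.5–94.4% | 91.7–94.3% |
| Type I error | 4.8–5.5% | 4.7–5.6% | 4.9–5.5% |
| Verdict at 0.05 differs | reference | 0.45–1.55% | 0.65–2.1% |

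Mean estimates differ by at most 0.001. The Monte Carlo standard error of a 5% rate is √(0.05 × 0.95/2000) = 0.5 points, so the type I error rates cannot be told apart. The largest SE increase (ratio 1.0088, step +0.5) would take a power of 92.1% to about Φ((1.960 + 1.412)/1.0088 − 1.960) = Φ(1.383) = 91.7%, a loss of less than half a point.

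*Week 24 ANCOVA simulation*, 192 subjects, 4,000 runs per scenario, steps 0, 0.2 and 0.5: mean SE 0.145–0.147 without the stratum and 0.145–0.146 with it; power 92.4–93.2% and 92.3–93.1%; type I error 5.0–5.4% and 5.1–5.6%. It agrees on the stratum but does not cover country or how often verdicts differ.

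**The case against.** The strongest reply is that the stratum is only a two-way cut of V5 HbA1c, the same measurement that enters as the continuous covariate, so the SAP already adjusts for it in finer form. Protocol 9.1 calls its own statistics a summary and makes the SAP final, so the sponsor may choose this model. The Appendix 1 code might also settle the terms. Verdicts differ in 0.85% of simulated trials even with an effect of −0.5 and no step at the cut, so much of that figure is the ordinary result of changing one term.

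Most of this stands. It removes any claim about the validity of the test and makes declaration an acceptable alternative to restoring the term. It does not make SAP 12 correct: permission to change a model is not a statement that nothing changed, and code could not cure that wording.

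Three stronger inferences are tempting and not supported:
- **That the imputation regression departs from the protocol.** SAP 8.1.2 gives an open list of explanatory variables, and Protocol 9.5.2 asks only for linear-regression multiple imputation without naming terms.
- **That the SAP dropped a promised MMRM excluding post-rescue values.** That analysis is in the synopsis but not in Protocol 9.5.1, whose three analyses SAP 8.1.2 follows. The conflict is mainly inside the protocol.
- **That LOCF definitely loses its visit terms.** The text says both that the MMRM is the same and that the list is shorter, so it is ambiguous.

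**Conclusion.** The point holds as a minor one. SAP 8.1.1 and the LOCF list omit the V5 HbA1c stratum, SAP 8.1.1 adds a conditional country term, and SAP 12 is not correct in saying that nothing changed. The wording mismatch is certain. What would actually be run is less so, because the Appendix 1 code was not in the text supplied.

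A reader might infer that the primary test is biased, loses meaningful power or has an inflated type I error. The documents do not support that: continuous baseline HbA1c stays in the model, and under the assumptions above the effect on the SE is below 1% in either direction. The practical consequence is that two documents define two primary p-values, which fell on different sides of 0.05 in about 0.5–2% of simulated trials.

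**What to change.** **Primary and LOCF models.** Add the V5 HbA1c stratum, as defined in SAP 3.7.1 and recorded in the IWRS, as a fixed effect beside continuous baseline HbA1c in SAP 8.1.1 and the LOCF model. If the sponsor prefers its own model, list the removal with the reason in SAP 12 before unblinding.

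**In either case:**
- Declare the conditional country term in SAP 12.
- Change the timing of the HbA1c stratum in SAP 3.4 and Protocol 3.1 to V5.
- State whether the LOCF model has visit and treatment-by-visit terms.
- Declare in SAP 12 the imputation-based sensitivity analyses on key secondary endpoints, the LOCF rule at rescue, and the safety grouping. Reconcile SAP 5.2 and Protocol 9.3.2 into one grouping rule.
- Reconcile the two lists of sensitivity analyses in the protocol synopsis and 9.5.1.
- Check the Appendix 1 code against the final term list.

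**Optional, and not a departure from the protocol.** If the stratum (and country, if triggered) is in the analysis model, put the same baseline covariates in the imputation models. Treatment is deliberately left out of the placebo-based step.

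**Cost.** SAP wording and one degree of freedom; the stratum is already in the IWRS data. The protocol corrections, if made by amendment, need IRB/IEC approval under Protocol 10.2. The sample size does not change.
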